During our development work, we engaged our team to identify and create the competing de-implementation strategies based on our prior qualitative research eliciting stakeholder input. We chose an ADT order check attestation (**Or**) versus an ADT provider script (**Sc**) as a communication aid to be used and documented as an accountable justification in the electronic medical record. Sites receiving the **Sc** intervention will also receive an educational handout that providers may elect to share with patients during clinic visits. Both strategies have a strong evidence-base for changing provider behavior and are tailored based on the COM-B and DCE survey. The work from pilot testing will play a critical role to help us understand the acceptability, feasibility, and scalability of these strategies in order to conduct the full-scale pilot randomized implementation trial. We will conduct pilots for up to six months across 3 VA sites and the pilot implementation trial across 4 VA sites.

The main goal of both interventions will be to decrease ongoing low-value ADT use for patients with prostate cancer, but to do this in a way that is acceptable to the clinicians who treat these patients. From a scientific perspective, we are purposely choosing to trial strategies from opposite ends of the behavior change continuum because of their evidence-based potential to change provider behavior. Specifically, we are selecting one approach (**Or**) that operates as an organizational constraint and a competing approach (**Sc**) that operates at an individual and dyadic level to build individual capacity, perceived to maximize ability of providers to communicate effectively. The first approach requires little to no learning on the part of providers, while the second requires upfront learning ("cost" to provider).

As illustrated in Figure 2, this approach sets up a testable hypothesis: that a blunt de-implementation organizational approach may be effective in the short-term, but that it will lose its effects as providers learn work-arounds. Conversely, an individual capacity building approach to de-implementation using a script might take longer to observe measurable decreases in castration rates, but its effects will create sustainable change as providers internalize and routinize this clinical practice.

STUDY DESIGN

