All 3 pilot test sites will be followed for up to 6 months. To implement the interventions and assess for issues in the implementation process in order to further refine the intervention plan, information will be collected regarding the process of ADT ordering at each site, including who is involved, through conversations with the Site Champion (who is also a project consultant) or their designee. Additionally, information regarding implementation status as well as any changes in site processes around prescribing ADT will be discussed at regular team meetings with the project consultants (including Site Champions). For both the pilot and implementation trial, outcomes will be collected from VA CDW/Cancer Registry/Vital Status/CMS records and CPRS/Capri/JLV/WebVRAM for all clinic visits documented as providing low-value ADT at baseline, 3 and 6 months. An organizational survey will be developed and refined throughout the pilot. For the pilot implementation trial, an anonymous clinic assessment survey will be administered to Site Champions at baseline and an ADT provider assessment will be administered to participating site providers at baseline and 1-month post-intervention through VA Qualtrics (Appendix VI).

Outcomes Analyses

Primary analyses: Comparing the effectiveness of two de-implementation strategies, **Or** vs. **Sc**, on continued low-value ADT use after six months. Our primary outcome is stopping ADT injections, which will likely be evaluated through a combination of chart reviews and informatics data generated through the ordering process. We will also explore the feasibility and impact of six-month outcomes during pilot testing to increase study efficiency and timeliness.

Secondary outcomes: RE-AIM implementation outcomes, changes from baseline measures, total ADT injections per arm at 6 months post implementation. (Table 4). We will examine moderators of strategy effectiveness (e.g., fidelity) and causal mechanisms underlying the strategies through content analysis from study team and pilot site meeting documents and discussion and based on our organizational assessment.

Table 4. Implementation Outcomes (based on the RE-AIM framework)

Domain	Order entry	Script
Reach	$(1 - \# \text{ ADT providers opt out}) / (\text{total ADT providers})$	$(1 - \# \text{ ADT provider opt out}) / (\text{total ADT providers})$

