Effectiveness *** (primary implementation outcome, and primary outcome of trial)	Low value ADT (LVADT) prescription order decrease $(\text{LVADT candidate expected orders} - \text{LVADT not ordered}) / (\text{LVADT got order} + \text{LVADT stopped order})$	
Adoption (provider level)	At least 1 order fired and signed (provider level)	At least 1 script signed (provider level)
Penetration Adoption (order level)	$(\# \text{ times order entry justified}) / (\# \text{ times order went through anyway})$	$\# \text{ scripts signed} / (\text{LVADT got order} + \text{LVADT stopped order})$
Implementation	Did implementation vary? 
- Differential adoption/penetration in medical oncology vs radiation oncology vs urology- Measure adoption/penetration at different time points (e.g., 3/6 months)- Number of sites that withdraw from participation (e.g., 3/6 month withdrawal rates)	
Fidelity	
- Were the justifications appropriate? (i.e., was something entered, or was no reasoning put in (enter n/a, etc))	
- Was the script edited? (i.e., not just signed)
Maintenance (site/setting level)	Proportion of sites that would elect to continue intervention, if available	

TIMELINE

R37 Funding: 1/1/2022 – 12/31/2023

PILOT SITE SELECTION

- The **Or** and **Sc** interventions will be piloted at the study PI and consultants' sites as follows:

Site	Site Champions	Intervention
VA Ann Arbor Healthcare System	[name] (co-PI)	Or & Sc
VA Greater Los Angeles Healthcare System	[name]	Or
VA New York Harbor Healthcare System	[name]	Or

PILOT SITE IMPLEMENTATION OVERVIEW

- Drs. [name], [name], and [name] are all consultants who have agreed to serve as Site Champions for the pilot work.
 - Study consultants do not have access to identifiable data or the study folder and are not "engaged" in study activities.
- Pilot sites will not be randomized.
- The ADT Order Check Attestation Intervention (**Or**) will be implemented at all sites, as this intervention requires engagement with other services, such as CAC, pharmacy, etc., and its procedures are most in need of refinement.
- The ADT Provider Script Intervention (**Sc**) will be implemented at Ann Arbor.
- The official start date for the pilot begins when we have started adding HF's and/or assigning progress notes. Pilot sites will be followed for up to 6 months.
- Facility Notifications & Approvals

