 1. Never had evidence of metastatic disease (including bones and lymph nodes)
 2. No treatment with CRPC medications (e.g., abiraterone, enzalutamide) in the last two years
 3. Has completed definitive treatment with radiation (+/- adjuvant ADT), RP, or cryotherapy
 4. Receiving ongoing ADT at the VA
 5. No rise in PSA level after definitive treatment
 - Current PSA ≤2 and not rapidly rising (no PSADT <10 months)

- Throughout the pilot, the data manager will complete data pulls at different time intervals (e.g., weekly, bi-weekly, monthly, etc.) to determine how often the data may need to be refreshed during the RCT. Data such as patient appointment cancellations, changes in PSA scores, new drug names, variations of appointments/treatments, etc. are important to keep updated as they can impact patient eligibility.

MPCA NATURAL LANGUAGE PROCESSING (NLP) TOOL USE IN VINCI

- We will use a validated NLP tool developed by the VA Salt Lake City Healthcare System Prostate Core to identify Veterans with metastatic prostate cancer (mPCa) in real time. This will enable us to further refine our cohort by excluding all mPCa patients.
 - The Prostate Core has provided a data dictionary for definitions of the variables.
 - We will inform the Prostate Core if any of our definitions are different (e.g., prostate cancer, mPCa, etc.).
 - In the event we find mPCa patients after we complete chart reviews, we will inform the Prostate Core team.
 - Study staff will view the NLP data output in a VINCI worksheet.

- The PCa Data Core table/list is updated monthly by VINCI (we should receive email notifications from VINCI when the list has been updated).

CHART REVIEWS

- Study staff will also **conduct chart reviews using CPRS/Capri/JLV/WebVRAM to confirm target ADT orders and clinic visits.**
 - Study staff will apply for local CPRS access at participating sites through WebVRAM, though Capri/JLV may also be used to conduct chart reviews

- As the ADT injections occur serially at 1, 3, or 6 month intervals, an individual provider could have multiple opportunities to be exposed to the intervention during the 6-month study period.

- Low-value ADT injections must have occurred within 14 months prior to data pull.

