Collection DT	Specimen	Test Name	Result	Units	Ref Range
01/18/2022 09:20	BLOOD	PSA	0.600	ng/mL	0 - 4
03/03/2022 08:00	BLOOD	PSA	0.200	ng/mL	0 - 4
06/25/2022 10:15	BLOOD	PSA	<0.100	ng/mL	0 - 4

ADT injections in the last 12 months:

Rx #	Stat	Qty	Issued	Last Filled	Rem
LEUPROLIDE (ELIGARD) 22.5MG(3 MONTH) LA INJ					
12824236	ACTIVE/SUSP	1	06/25/2022	06/25/2022	(1)

For this clinical scenario, where the harms of ADT likely outweigh the benefits, NCCN (tinyurl.com/2p9f5w8r) and AUA guidelines (tinyurl.com/4ueptrtd) recommend either transitioning to intermittent ADT or discontinuation of ADT.

Talking points:

-We are learning more about prostate cancer all the time, and continue to update recommendations based on new information. Since hormone therapy comes with long-term effects on your health, I'm worried the harms are greater than the benefit.

-Hormone treatment can have long-term effects that you don't notice right away, like thinning bones, diabetes, and heart disease. Most patients don't notice these conditions until they have a complication like a broken hip.

-If we get any indication that your prostate cancer is behaving more aggressively or causing you problems, we may decide the benefits of hormone therapy are greater than the harms. We can restart the hormone therapy at any point.

Patient information sheet - "Living Well with Prostate Cancer: Is Hormone Therapy Still Right for You?"

tinyurl.com/bdh45bnn

Patient prefers to:

Continue ADT

OR

Discontinue ADT and follow up in 3-6 months with a PSA test

Updated 7/27/2023 – changes made to information displayed in the ADT injections section.

Advisory: ADT for Localized/Non-Metastatic Prostate Cancer

Based on multidisciplinary review, this patient appears to be on ADT as treatment for biochemically recurrent prostate cancer.

Most recent PSA values:

Collection DT	Specimen	Test Name	Result	Units	Ref Range
06/20/2023 09:54	SERUM	PSA	0.19	ng/mL	0 - 4
11/05/2022 09:22	SERUM	PSA	0.57	ng/mL	0 - 4
08/16/2021 09:16	SERUM	PSA	1.06	ng/mL	0 - 4

ADT injections in the last 12 months:

LEUPROLIDE (ELIGARD) 45mg given SQ in Right side of abdomen Administered 06/20/2023
Expiration date / Lot#: [mmm]/[yyyy] Lot [xxxxxx]A1

LEUPROLIDE (ELIGARD) 45mg given SQ in Left side of abdomen 11/05/2022
Expiration date / Lot#: [mmm]/[yyyy] Lot [xxxxxx]A1

LEUPROLIDE (ELIGARD) 45mg given SQ in Right side of abdomen 08/16/2021
Expiration date / Lot#: [mmm]/[yyyy] Lot [xxxxxx]A1

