- 1) Dial study phone number (from jabber or any phone)
- 2) Once voicemail starts, select *
- 3) Instruction's state: "Enter your ID followed by pound" enter phone number: **xxxxx#**
- 4) Instruction's state: "Enter your pin followed by pound" enter pin: **xxxxx#**

(Note: PIN #'s are required to be changed often, study staff will add a 1 to pin each time it needs to be updated.

PILOT STUDY FLOW CHART

PILOT RANDOMIZED IMPLEMENTATION TRIAL

TRIAL SITE SELECTION

- We will update national VA and Medicare data to identify eligible sites for the cRCT.
- All VA sites with high rates of low-value ADT from 2020 – 2022 will be considered eligible to participate in the study.
- We will start with the 40 facilities with the highest rates of low-value ADT and continue down the list as necessary.
- We will exclude sites requiring translated materials (e.g., Puerto Rico).
- If feasible, we will exclude sites scheduled to transition to Cerner prior to the end of the cRCT.
- We will randomize 4 VA facilities with high rates of low-value ADT use.

TRIAL SITE RECRUITMENT & RANDOMIZATION

- The top 4 sites with high rates of low-value ADT use and meeting above criteria will be invited to participate in the study.
- All invited sites that agree to participate will be included.
- We expect 80% participation by eligible sites.
- If sites are unwilling or unable to participate, we will continue down the list of sites until we reach a maximum of 4 participating sites.
- Study staff will send an email from the study Co-PI to Urology Chiefs to recruit as Site Champions.
 - If we are unable to contact Urology Chiefs, or if we do not receive a response from the Urology Chief after two formal email contacts, we may reach out to the Chief of Surgery, Chief of Med/Onc, or Chief of Rad/Onc (and copy the ACOS/R) about serving as Site Champion.
 - If the Urology Chief declines to serve as Site Champion, we may ask if they have any suggestions for an alternate designee.
 - In the event we are unable to recruit a Site Champion, all Site Champion communications will come from the study team.
- Once Site Champions have obtained approval from the MCD, each site will be randomized to the **Or** or **Sc** arm. The Data Manager will work with our Consultant, [name] on randomizing sites.

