 - Our current plan will be to stratify sites by availability of Radiation Oncology to ensure there is an even distribution of Radiation Oncology in both intervention arms. We intend to randomize sites in blocks of 2-4.
- Once site Clinical Health Information Officer has agreed to implementation the intervention at their site, study staff will apply for site CPRS access.
 - Note: Once you have CPRS access for a site, set an Outlook reminder to log in to each site every 30 days.

TRIAL OR/Sc IMPLEMENTATION

- Implementation procedures will be similar to those of the pilot but refined as needed based on pilot outcomes and needs specific to trial site implementation.
- Interventions will be implemented for up to 12 months at each site.
- Study staff will apply for CPRS access at each site once we receive approval from either the Medical Center Director or Site Champion.
- Baseline ADT Prescribing Meetings – these meetings with Site Champions or their designees will not be mandatory for the RCT. We will move forward with our trial implementation even if we haven't collected information regarding the ADT ordering process.

- Implementation Education Session (IES) – to make scheduling easier on the study team, we may implement one IES per site instead of each department. We will move forward with implementing the interventions after scheduled IES's, even if they have been cancelled.
- There is a possibility that patients will receive ADT injections more than once during the intervention period. If this is the case, then the intervention will be triggered more than once for the same patient.

TRIAL DATA COLLECTION

- Data sources for our primary, implementation and secondary fidelity outcomes will be refined during the pilot. Data collection and outcomes analyses plan will also be further developed during the pilot.
- We will likely assess **Or** fidelity using informatics data generated through the ordering process.
- We will use chart review to identify **Sc** documentation in the EMR, in addition to other informatics approaches.

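### The secondary outcome is an undenominated total of injections per arm, although one injection covers 1, 3 or 6 months; Table 4's order-based Effectiveness ratio is partly exposed to the same problem

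*Protocol*

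**What the plan says.** Under Outcomes Analyses, the protocol states "Our primary outcome is stopping ADT injections" and lists among the secondary outcomes "total ADT injections per arm at 6 months post implementation". No denominator is given for that total. The same sentence also lists changes from baseline measures.

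Table 4 labels Effectiveness as the primary outcome of the trial and heads it "Low value ADT (LVADT) prescription order decrease". The formula is expected orders minus those not ordered, divided by orders obtained plus orders stopped. The terms expected and stopped are not defined.

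On timing, the Chart Reviews section says "As the ADT injections occur serially at 1, 3, or 6 month intervals". Trial Or/Sc Implementation adds "There is a possibility that patients will receive ADT injections more than once during the intervention period". The progress note template shows one such product, "LEUPROLIDE (ELIGARD) 22.5MG(3 MONTH) LA INJ".

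On allocation, Trial Site Selection says "We will randomize 4 VA facilities with high rates of low-value ADT use". Trial Site Recruitment & Randomization stratifies on availability of Radiation Oncology only. The matching on patient numbers in Trial Data Collection is between intervention and control sites, not between Or and Sc.

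**The concern.** The trial asks whether low-value ADT is reduced. An injection is not a fixed amount of ADT: over 6 months one continuously treated man is due 6 injections on monthly dosing, 2 on 3-monthly and 1 on 6-monthly. A raw total therefore mixes three things with de-implementation: how many eligible patients the arm has, which products its sites use, and whether a product is changed during the trial.

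With about two sites per arm and no balancing on size or product mix, the first two will not average out. The third would be scored as success although ADT continues. Table 4 shares the order unit, so part of the problem reaches the measure labelled primary.

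**Working it through.** **Inputs.** From the protocol: intervals of 1, 3 or 6 months, a 6-month window, 4 sites in two arms. The protocol gives no patient numbers, interval mix or stopping rate, so there is no stated figure to reproduce. The patient numbers, mixes, switch shares and stopping rates below are assumptions.

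**Raw total.** Injections due in the window = patients × (1 − share stopped) × 6 / interval in months.

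| Scenario | Calculation | Total |
|---|---|---|
| 60 patients, monthly, none stop | 60 × 6 | 360 |
| 60 patients, 3-monthly, none stop | 60 × 2 | 120 |
| 60 patients, 6-monthly, none stop | 60 × 1 | 60 |
| 40 patients, 3-monthly, none stop | 40 × 2 | 80 |
| 60 patients, 20/60/20% on 1/3/6 months, none stop | 72 + 72 + 12 | 156 |
| 60 patients, 0/50/50% on 1/3/6 months, none stop | 60 + 30 | 90 |
| 60 patients, monthly, 30% stop | 42 × 6 | 252 |

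- Arm size: 80 against 120 is 33% lower.
- Interval mix: 90 against 156 is 42% lower.
- Direction: an arm on monthly dosing in which 30% stop (252) still totals more than a 3-monthly arm in which nobody stops (120).
- Switching 10%, 25%, 50% or 100% of 60 patients from 3-monthly to 6-monthly gives 114, 105, 90 or 60 against 120. These are falls of 5%, 12.5%, 25% and 50% with unbroken cover.

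**Change from baseline.** With none stopping and stable dosing, the change is 0 in an arm of either size. With 30% stopping, 120 falls to 84 and 80 falls to 56. The relative change is −30% in both, but the absolute change is −36 against −24. A switch during the trial still appears as a fall (120 to 90).

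**Table 4 ratio.** Take 60 patients, half of whom stop at the first due order. The share of orders not placed is stopped / (obtained + stopped).

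| Interval | Each stop logged as one order | Every missed due order logged |
|---|---|---|
| Monthly | 30 / (180 + 30) = 14% | 180 / 360 = 50% |
| 3-monthly | 30 / (60 + 30) = 33% | 60 / 120 = 50% |
| 6-monthly | 30 / (30 + 30) = 50% | 30 / 60 = 50% |

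The second convention removes the interval effect only when stopping is the same at every interval. With 10 monthly and 40 six-monthly patients (60 + 40 = 100 due orders), if only the monthly patients stop, 60% of orders disappear but 10 / 50 = 20% of patients stopped.

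For switching, let expected orders be set at the 3-monthly rate (120) and half the patients move to 6-monthly, so that 30 orders are not placed. If those 30 enter the denominator as stopped, the ratio is (120 − 30) / (90 + 30) = 0.75 with nobody stopping. If they do not, it is (120 − 30) / (90 + 0) = 1.00.

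Arm size cancels. With 40 patients and half switching, the first convention gives (80 − 20) / (60 + 20) = 0.75 again.

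**Per-patient measures.** In every no-stopping scenario above, the share stopped is 0% and cover is 6 months per patient, whatever the interval, arm size or switch.

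**The case against.** The strongest reply is that the primary outcome is sound. Stopping injections, checked by chart review, reads naturally as a patient event, and Table 4 is a ratio with a term for expected orders. Much of this stands. A reader might infer that the primary outcome as a whole is invalid, or that arm size distorts it. The protocol does not support either: arm size cancels in Table 4, and under one counting convention uniform stopping gives the same answer at all intervals. What remains is that the protocol does not fix the patient-level reading and that Table 4 counts orders.

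A reader might also infer that providers at Or sites are expected to lengthen intervals to avoid the check, because the Study Overview says of the blunt approach that "it will lose its effects as providers learn work-arounds". That sentence predicts a fading effect, not a false success, and the check can be overridden by entering a number or text. Switching can move these measures, but nothing in the protocol shows that it will happen.

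Three further points carry weight. Change from baseline partly offsets stable differences between sites, though not switching. The Site Champion assessment in Appendix VI asks about usual injection frequency, so interval information is sought, but nothing says it enters the outcome. The protocol also says that outcome measures and analyses will be refined during the pilot. That lowers the seriousness, but the objection is to a measure already named: an analysis that followed it faithfully would inherit the fault.

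Finally, every mix is assumed. The product examples in the protocol include a 3-month injection and none labelled monthly, so the six-fold range is an outer limit.

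**Conclusion.** The point holds in full for the secondary outcome. Arm size, interval mix and product switching each move the total with no de-implementation, and neither the stratification nor the control-site matching balances them between Or and Sc. Illustrative sizes are 33% for 60 versus 40 patients, 42% for one pair of interval mixes, and 25% if half of 3-monthly patients switch. True sizes depend on numbers that the protocol does not give.

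It holds in part for Table 4 Effectiveness. Arm size has no effect. Interval, stopping that differs between intervals, and switching can distort it, depending on how the undefined expected and stopped orders are counted. This should be corrected before outcomes are abstracted, but it does not show that the primary comparison is biased.

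**What to change.** 1. **Primary outcome.** Score it once per eligible patient: ADT stopped or not at read-out, judged by whether the labelled cover of the last injection has lapsed without renewal. Rewrite the Effectiveness row of Table 4 to match.
2. **Secondary outcome.** Replace the total with months of ADT cover within the 6-month window, summed over patients and divided by the number of eligible patients. Truncate cover at the window end and carry in cover from injections given before launch. Otherwise a 6-month injection on the last day scores 6 months, and one given the day before launch scores none. Calculate it the same way at baseline and at control sites. Keep the raw total as descriptive only.
3. **Classification.** Count a switch to a longer-acting product with continuous cover as continuing. Record a transition to intermittent ADT as its own category, since the order check and the progress note both present it alongside discontinuation. This concerns scoring only and takes no position on which product or schedule is appropriate.

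**Cost.** Beyond the wording, staff must abstract product and date for each injection. The Sc note instructions already gather these for patients who receive a note, but the chart review form shows only the most recent injection, so Or and control-site patients need modest extra work. One limit remains: a patient on 6-monthly dosing whose cover spans most of the window has little time to show a lapse, and the read-out should say so.
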